Appendix 4. Response assessment in ALL

Assessment of clinical response will be made according to NCCN guidelines on ALL Version 2. 2016 with the exception of Partial Remission, Overall Response Rate, Refractory Disease, and Relapsed Disease. The major criteria for judging response will include physical examination and examination of blood and bone marrow. All laboratory studies that are abnormal prior to study will be repeated to document the degree of maximal response.

Response criteria for blood and bone marrow

Complete Remission (CR)

CR requires all of the following:

- No circulating blasts or extramedullary disease (no lymphadenopathy, splenomegaly, skin/gum infiltration/testicular mass/CNS involvement
- Trilineage hematopoiesis (TLH) and < 5% blasts in bone marrow aspirate.
- Absolute Neutrophil Count (ANC) > 1,000/uL.
- Platelets > 100,000/uL.

CR with incomplete blood count recovery (CRi)

CRi meets all criteria for CR except platelet count and/or ANC:

• Platelets $\leq 100, 000/ \text{ uL}$ and/or ANC is $\leq 1,000/\text{uL}$

Overall response rate (ORR=CR+CRi+PR)

Partial Remission (PR)

Note: PR is not defined per NCCN guidelines but defined in this protocol. PR requires all of the following: Meets all criteria for CR except for BM blasts:

• bone marrow may contain \geq 5% but less than 25% blast morphology

Refractory disease: Failure to achieve CR, CRi or PR at the end of induction

Progressive disease (PD): increase of at least 25% in the absolute number of circulating or bone marrow blasts or development of extramedullary disease

Relapsed disease: reappearance of blasts in the blood or bone marrow (> 5%) or in any extramedullary site after a CR / CRi/PR.

Response criteria for mediastinal/extramedullary disease:

CR: Complete resolution of mediastinal enlargement or extramedullary mass/es by CT. For patients with a previous positive PET scan, a post-treatment residual mass of any size is considered as CRE as long as it is PET negative.

PR: > 50% decrease in the SPD of the mediastinal enlargement or extramedullary mass/es from baseline. For patients with a previous positive PET scan, post-treatment PET must be positive in at least one previously involved site.

PD: > 25% increase in the SPD of the mediastinal enlargement or extramedullary mass/es from nadir or development new mediastinal/extramedullary mass/es. For patients with a previous positive PET scan, post-treatment PET must be positive in at least one previously involved site.

No Response (NR): failure to quantify for CR, PR or PD

Relapse: Recurrence of mediastinal enlargement after achieving CR. For patients with a previous positive PET scan, post-treatment PET must be positive in at least one previously involved site.

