4. SUBJECT POPULATION

4.1. Number of Subjects and Subject Selection

4.2. Inclusion Criteria

Subjects must meet all of the following inclusion criteria to be eligible for participation in this study.

- 1) ≥ 18 years of age
- 2) Previously treated ALL including Philadelphia chromosome (BCR-Abl) positive ALL who meet all of the following criteria:
 - a) Diagnosis of precursor B-cell ALL based on flow cytometry and histology
 - b) Previously treated subjects with primary refractory disease OR after first or subsequent relapse
 - c) Subjects with >10% lymphoblasts in bone marrow (BM) or extramedullary disease (EMD) that is radiographically measureable and amenable to imaging studies and repeat biopsies
 - d) Patients with Ph+ ALL must have failed treatment with at least one 2nd generation (ex. dasatanib) or 3rd generation (ex. ponatinib) tyrosine kinase inhibitor
- 3) Eastern Cooperative Oncology Group (ECOG) performance status ≤ 2
- 4) Adequate organ function defined by the screening laboratory inclusion values (Table 4-1) and absence of known cardiac dysfunction
- 5) Required screening laboratory data (within 7 days prior to administration of GS-9973) as shown in (Table 4-1) Note: Confirmation should be considered for out-of-range values to determine if the abnormality is real or artifactual. Values should be obtained within the screening period and should be the most recent measurement obtained

Organ System	Parameter	Required Value
Hepatic	Serum total bilirubin	<2.0 mg/dL or ≤ 1.5 x ULN (unless elevated due to Gilbert's syndrome)
	AST (SGOT)	\leq 2.5 x institutional ULN (unless due to disease then < 5 x ULN)
	ALT (SGPT)	
Renal	Creatinine	<2.0mg/dL
Pregnancy	β-HCG ^a	Negative
Infection ^c	HIV ^b	Negative HIV antibody/PCR
	HBV	Negative HBsAg and negative HBc antibody or positive HBc and negative HBV DNA by quantitative PCR
	HCV	Negative viral RNA (if HCV antibody is positive)

Table 4-1.Required Screening Laboratory Values

a For women of childbearing potential only; serum β-HCG must be negative during screening and serum β-HCG or urine dipstick pregnancy test must be negative at start of study drug

b If screening test is positive, a negative confirmatory test will be required for eligibility

c Screening for infection can be done up to 30 days prior to administration of study drug

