1.2. Study Design

This is an open-label, Phase 1b dose-escalation and Phase 2 expansion study evaluating the safety, efficacy, tolerability, and PK of ENTO in combination with VCR and dexamethasone.

The study was originally designed for 2 stages sequentially: (1) Phase 1b dose escalation; (2) Phase 2 expansion. However, due to the low response rate to ENTO in combination with VCR and dexamethasone in Phase 1b portion, per the Sponsor’s decision, it has been decided not to proceed with the dose expansion (ie, Phase 2) portion of this study.

There are four dose levels in the dose escalation phase (Table 1-1) where subjects in cohorts of 3 to 6 are sequentially enrolled into one of the dose levels using a 3+3 dose escalation design (Table 1-2). The starting dose level for the first cohort is defined as Dose Level 1.

Table 1-1 Entospletinib/Vincristine Dose Escalation

Dose Level	Entospletinib (ENTO)	Vincristine (VCR)
1	200 mg BID	0.5 mg per dose
2	400 mg BID	0.5 mg per dose
3	400 mg BID	1 mg per dose
4	400 mg BID	2 mg per dose

BID = twice per day

Dose Escalation: Induction (Lead-in, Cycle 1 and Cycle 2)

Lead-in (ENTO Monotherapy): Beginning on Day -7 of Lead-In, ENTO will be administered orally twice daily (BID) for 7 days as a single agent.

Cycle 1 and Cycle 2 (ENTO, VCR, dexamethasone, CNS prophylaxis)

[figure not shown]
ENTO will be continuously administered orally BID in combination with chemotherapy for the duration of the study treatment.

VCR will be administered on Days 1, 8, 15 and 22 of each 28-day cycle for Cycle 1 and 2 only.

Dexamethasone (20 mg twice daily for 4 days) will be administered orally during Cycle 1 on Days 8-11 and Days 22-25 and during Cycle 2 on Days 1-4 and Days 15-18.

CNS prophylaxis per institutional standard will be given on Day 28 (± 3 days) of Cycle 1 and Cycle 2.

Dose Escalation treatment schedule is outlined in the schema below:

Bone marrow (BM) aspirate/biopsy will be performed during screening (within 28 days prior to the start of study treatment), Cycle 1 on Day 8 and during both Cycle 1 and Cycle 2 on Day 28.

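### Marrow PR has no baseline comparison and no ranking against relapse, so an unchanged marrow can count in PR rate and ORR, and one relapsed after CR/CRi can count in ORR

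*Protocol*

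**What the plan says.** - **Marrow PR** (Protocol Appendix 4). The rule is "Meets all criteria for CR except for BM blasts", and the marrow may hold at least "5% but less than 25% blast morphology". The appendix notes that this category is the protocol's own, because NCCN does not define it. The other CR criteria are no circulating blasts or extramedullary disease (EMD), trilineage hematopoiesis, ANC above 1,000/uL and platelets above 100,000/uL.
- **Extramedullary PR** (same appendix). This needs more than a "50% decrease in the SPD of the mediastinal enlargement or extramedullary mass/es from baseline".
- **Entry** (Protocol 4.2, criterion 2c). "Subjects with >10% lymphoblasts in bone marrow (BM) or extramedullary disease (EMD") that can be measured. Table 4-1 sets no minimum ANC or platelet count.
- **Relapse** (Appendix 4). "reappearance of blasts in the blood or bone marrow (> 5%) or in any extramedullary site after a CR / CRi/PR".
- **Marrow schedule** (SAP 1.2). After screening, marrow is sampled at "Cycle 1 on Day 8 and during both Cycle 1 and Cycle 2 on Day 28".
- **Rates** (Protocol 8.1.3, SAP 6.2.1). CR, CR/CRi and ORR are defined at end of induction. The PR rate is named as an end-of-induction rate but defined by best response. SAP 6.2.2 uses end of induction for all four and orders response only against other anticancer therapy and transplant.
- **Source of the definition.** Protocol 8.1.3 points to Appendix 4 for marrow PR. SAP 6 and 6.2.1 cite only NCCN version 2.2016, whose marrow criteria (Protocol Appendix 7) contain no PR.

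**The concern.** Marrow PR describes a state at one visit, not a change. Its blast range overlaps the range in which a subject may enter, so a subject whose marrow has not moved can satisfy it. Its range also overlaps the relapse threshold, and neither document says which category wins when both fit.

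PR rate and ORR are two of the four secondary response rates, and they are tabulated by dose level with very small denominators. SAP 1 says that Phase 2 was dropped because of a low response rate, so responders are likely to be few and whether each is a real response matters to anyone reading the table.

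**Working it through.** **1. Unchanged marrow.** Let b be the baseline marrow blast percentage.
- Entry through marrow disease: b > 10.
- Marrow PR at the assessment: 5 ≤ blasts < 25, other CR criteria met.
- With no change, both hold when 10 < b < 25.

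Example: 15% at screening and 15% at Cycle 2 Day 28, with no circulating blasts or EMD, trilineage hematopoiesis and adequate counts. The change is zero and the category is PR.

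CR has no such gap. It needs blasts below 5%, which does not overlap entry above 10%, so for a marrow-eligible subject CR implies a fall even though it is also defined by state.

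**2. Relapse after CR/CRi.** Relapse needs blasts > 5% after remission; PR needs 5 ≤ blasts < 25. Both hold when 5 < blasts < 25. Example: CR at Cycle 1 Day 28, then 15% at Cycle 2 Day 28 with the other CR criteria met.

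| Rate | Timing in its definition | Can this subject count? |
|---|---|---|
| CR; CR/CRi | End of induction | No, 15% fails the blast criterion |
| ORR | End of induction | Yes, through PR |
| PR rate | End of induction and best response | Only if end of induction governs; on best response the subject is CR/CRi |

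**3. Size.** The planned denominator reproduces: 3 + 3 + 6 + 6 = 18 and 18/(1 − 0.10) = 20 (SAP 1.3). No stated figure in the plan depends on the PR definition. The effect of one subject, with exact (Clopper-Pearson) 95% intervals, the method named in Protocol 8.5.1:

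| n | 0 responders | 1 responder | Shift |
|---|---|---|---|
| 20 | 0% (0 to 16.8) | 5.0% (0.1 to 24.9) | 1/20 = 5.0 points |
| 6 | 0% (0 to 45.9) | 16.7% (0.4 to 64.1) | 1/6 = 16.7 points |
| 3 | 0% (0 to 70.8) | 33.3% (0.8 to 90.6) | 1/3 = 33.3 points |

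**4. How likely.** The documents do not give the share q of subjects who would meet PR at baseline and stay unchanged. As an assumption only, the chance of at least one among 20 is 1 − (1 − q)^20: 33% at q = 2%, 64% at 5%, 88% at 10% and 99% at 20%. At q = 0 it is zero.

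**The case against.** The strongest defence is that PR was openly constructed for this protocol, on the same state-based pattern as CR and CRi, and that its remaining conditions are demanding. Few relapsed or refractory subjects will have recovered counts, trilineage hematopoiesis and no circulating blasts while their marrow is unchanged. Investigators assess response and may not call such a case PR. The relapse path is narrower still: Protocol 3.3.3 expects most subjects reaching CR to go to transplant, and SAP 6.2.2 takes response on or before that. The rates are descriptive, the report is synoptic, and Phase 2 is already cancelled.

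All of that limits frequency and consequence, and it stands. It does not close the gap. The parallel with CR fails because CR cannot overlap the marrow entry range and PR can. No written rule tells an investigator to reject an unchanged marrow.

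A reader might also infer more than the documents support:
- *A marrow relapsed after CR/CRi counts in both rates.* Only ORR is clearly affected, because the PR-rate definition also says best response.
- *PR overlaps progressive disease.* Marrow progression is an "increase of at least 25% in the absolute number of circulating or bone marrow blasts or development of extramedullary disease", with no reference point stated, whereas the extramedullary rule speaks of an "increase in the SPD of the mediastinal enlargement or extramedullary mass/es from nadir". An overlap appears only if one assumes a rise relative to baseline and lets marrow percentage stand in for absolute number.
- *A sustained PR is itself relapse, since its blasts exceed 5%.* Relapse requires reappearance. Blasts of 10% at both Day 28 marrows are persistence.
- *The rates must be biased upward.* A fall from 80% to 10%, (80 − 10)/80 = 87.5%, with platelets of 90,000/uL is not PR, so the definition can also understate response.
- *The listing will hide blast percentages.* SAP 6.2.2 does not itemise its columns, and Protocol 8.3 plans listings of important variables. Blast percentages are not assured, but they are not excluded.

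**Conclusion.** The point holds in limited form. Followed as written, Appendix 4 lets a subject entering above 10% and below 25% blasts count in PR rate and ORR with no marrow improvement. It also lets a subject who relapsed from CR/CRi during induction count in ORR, and in the PR rate only if end of induction overrides best response, which the documents leave open.

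One such subject is worth 5.0 points at the planned 20, and 16.7 or 33.3 points within a dose level. These sizes rest on planned numbers; the actual number affected is not given and may be zero. The CR and CR/CRi rates, the primary safety endpoint and the sample size are unaffected. It is worth correcting because the repair is small and responses are expected to be few.

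The SAP's missing pointer to Appendix 4 is only a cross-reference to restore: the definition is still reachable through SAP 1, which rests on Amendment 5, and Protocol 8.5.

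**What to change.** For the analysis only, in SAP 6.2.1 and 6.2.2:

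1. Use end of induction for all four rates, with PR as best response in a separate row if wanted. Cite Protocol Appendix 4 for marrow PR.
2. Keep the investigator-assessed PR rate and ORR under the Appendix 4 definition as the main result, with no recorded PR removed. Taking PRs out of the main rates once the low response rate is known would be harder to defend than the gap itself.
3. Add one supplementary row each for PR rate and ORR, counting marrow PR only if blasts fell from baseline and the subject had not relapsed after CR/CRi. EMD-only subjects stay on the imaging rule. A missing baseline or end-of-induction value counts as no PR, in line with how Protocol 8.5.1 treats overall remission. Since item 1 lets a relapsed subject recorded as PR into the main PR rate, this row shows the rate without that subject.
4. List baseline and end-of-induction blast percentages for each PR. The supplementary row accepts any fall, even 24% to 23%, so the listing lets readers judge its size.
5. State in the CSR that the change was made after the low response rate was known.

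The cost is a few lines of SAP text, two table rows and two listing columns. Blast percentages may have to come from local marrow reports (Protocol 6.2.7), because the documents do not say that the eCRF holds them. The supplementary rates may be slightly lower than the main ones.

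Where PR or relapse also drives treatment decisions (Protocol synopsis on duration of treatment, 3.3.1.1, 3.3.3 and 6.6), the passages are for the sponsor to reconcile. No clinical rule is proposed here.

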Duration of Treatment:	Subjects may continue receiving GS-9973 until refractory disease at the end of induction, relapsed disease, start of new therapy, unacceptable toxicity, withdrawal of consent by subject, or withdrawal from study by investigator.
Diagnosis	Inclusion Criteria
and Main Eligibility Criteria:	Subjects must meet all of the following inclusion criteria to be eligible for participation in this study:
(see	1) ≥ 18 years of age
Protocol for Details)	2) Previously treated ALL including Philadelphia chromosome (BCR-Abl) positive ALL who meet all of the following criteria:
	a) Diagnosis of precursor B-cell ALL based on flow cytometry and histology
	b) Previously treated subjects with primary refractory disease OR after first or subsequent relapse
	c) Subjects with >10% lymphoblasts in bone marrow or extramedullary disease (EMD) that is radiographically measureable and amenable to imaging studies and repeat biopsies
	 d) Patients with Ph+ ALL must have failed treatment with at least one 2nd generation (eg. dasatanib) or 3rd generation (eg. ponatinib) tyrosine kinase inhibitor

- 3) Eastern Cooperative Oncology Group (ECOG) performance status ≤ 2
- 4) Adequate organ function defined by the screening laboratory value inclusion and absence of known cardiac dysfunction
- 5) Required screening laboratory data (within 7 days prior to administration of GS-9973) (Table 4-1)
- 6) Discontinuation of all therapy (including radiotherapy, chemotherapy, tyrosine-kinase inhibitors [TKIs], immunotherapy, or investigational therapy) for the treatment of cancer as follows:
 - a) At least 1 week or 5 half-lives (whichever is longer) from the last dose of prior anti-cancer therapy and the initiation of study therapy
 - b) Exceptions or modifications to the above are as follows: Medications that are typically part of a maintenance therapy for ALL, such as glucocorticoids or mercaptopurine, may be administered up to 3 days prior to the first dose, except vinca alkaloids which must be discontinued at least 14 days prior to the start of study treatment. TKIs are not permitted to be continued at screening (eg, Gleevec). Subjects may receive hydroxyurea or leukapheresis if indicated for rapidly rising white blood cell count
 - c) CNS prophylaxis should be dosed up at least one week prior to first dose of GS-9973
 - d) For biologics (eg, monoclonal antibodies), washout period of at least 4 weeks or 5 half-lives (whichever is shorter) since the last dose

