3.3.3. Maintenance

It is anticipated that most subjects will receive hematopoietic stem cell transplant (HSCT) therapy with curative intent if a complete remission (CR) is reached. In the absence of suitable alternative therapeutic options, subjects who obtain clinical benefit (at least PR) after completing both cycles of induction therapy in dose escalation may continue GS-9973 at the assigned dose level in the maintenance phase for up to 36 cycles. Subjects will continue GS-9973 and VCR at their assigned dose. GS-9973 will continue to be taken orally twice daily with VCR given on Day 1 of each 28-day cycle. Dexamethasone may be administered as a single dose of 20 mg once daily or a divided dose of 10 mg twice daily on Days 1-4 and Days 15-18 of each 28-day cycle.

Bone marrow evaluations and additional central nervous system (CNS) directed therapy can be performed as clinically indicated in the maintenance phase.

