Appendix 7.NCCN Guidelines (version 2.2016)

Response assessment

Response Criteria for Blood and Bone Marrow:

- Complete Response (CR):
 - No circulating blasts or extramedullary disease
 - No Lymphadenopathy, splenomegaly, skin/gum infiltration/testicular mass/CNS involvement
 - ➤ Trilineage hematopoiesis (TLH) and <5% blasts
 - ➤ Absolute neutrophil count (ANC) >1000/microL
 - Platelets >100,000/micro/L
 - ➢ No recurrence for 4 weeks
- Complete Response with incomplete blood count recovery (CRi):
 Meets all criteria for CR except platelet count and/or ANC
- Overall response rate (ORR = CR + CRi)
- Refractory disease
 - ➢ Failure to achieve CR at the end of induction
- Progressive disease (PD)
 - Increase of at least 25% in the absolute number of circulating or bone marrow blasts or development of extramedullary disease
- Relapsed disease
 - Reappearance of blasts in the blood or bone marrow (>5%) or in any extramedullary site after a CR

Response Criteria for Mediastinal Disease

- CT of chest with IV contrast and PET imaging should be performed to assess response
- CR: Complete resolution of mediastinal enlargement by CT. For patients with a previous positive PET scan, a post-treatment residual mass of any size is considered a CR as long as it is PET negative
- PR: >50% decrease in the sum of the product of the greatest perpendicular diameters (SPD) of the mediastinal enlargement. For patients with a previous positive PET scan, post-treatment PET must be positive in at least one previously involved site
- PD: >25% increase in the SPD of the mediastinal enlargement. For patients with a previous positive PET scan, post-treatment PET must be positive in at least one previously involved site
- No Response (NR): failure to qualify for PR or PD
- Relapse: recurrence of mediastinal enlargement after achieving CR. For patients with a previous positive PET scan, post-treatment PET must be positive in at least one previously involved site

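### Appendix 4 applies a >5% marrow limit for relapse after partial remission, although a PR marrow holds 5% to under 25% blasts by definition

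*Protocol*

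**What the plan says.** Protocol Appendix 4 gives three definitions that meet here.

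- **CR** requires, among other things, "Trilineage hematopoiesis (TLH) and < 5% blasts in bone marrow aspirate".
- **Marrow PR** "Meets all criteria for CR except for BM blasts", where the marrow may hold at least "5% but less than 25% blast morphology".
- **Relapsed disease** is "reappearance of blasts in the blood or bone marrow (> 5%) or in any extramedullary site after a CR / CRi/PR".

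The guideline text reproduced in Appendix 7 uses the same marrow limit but starts from CR alone: "Reappearance of blasts in the blood or bone marrow (>5%) or in any extramedullary site after a CR". Appendix 4 announces that its PR, overall response, refractory and relapse definitions depart from the guideline. Its separate relapse rule for mediastinal and extramedullary disease still starts from CR only.

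Two treatment passages use these labels. Section 3.3.3 says that "subjects who obtain clinical benefit (at least PR) after completing both cycles of induction therapy in dose escalation may continue GS-9973". The synopsis, under Duration of Treatment, says "Subjects may continue receiving GS-9973 until refractory disease at the end of induction, relapsed disease, start of new therapy".

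Protocol Section 8.5.1 plans RFS, EFS and cumulative incidence of relapse. SAP Section 6 cites the guideline criteria and does not restate the Appendix 4 relapse rule.

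**The concern.** The guideline's >5% limit separates relapse from remission because a subject in CR starts below 5%. Appendix 4 added CRi and PR as starting states and left the limit where it was. A CRi marrow is also below 5%, so that addition does no harm. A PR marrow starts at or above the limit, so the limit cannot separate a PR that is holding from one that has been lost. Appendix 4 gives no nadir, required increase or separate limit for relapse from PR.

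Two things are at stake. First, in any relapse-based analysis that admits PR subjects, the event date could be set by when the next marrow was taken, not by any worsening. Second, the same unchanged marrow can be read as a response that qualifies for maintenance and as relapsed disease that ends treatment.

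**Working it through.** There is no stated figure to reproduce; the check compares thresholds.

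**Inputs (Appendix 4), marrow blasts b in percent**

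- CR/CRi: b < 5
- PR: 5 ≤ b < 25, all other CR criteria met
- Relapse, marrow part: b > 5 after CR, CRi or PR
- PD: an increase of at least 25%, taken here as b₂ ≥ 1.25 × b₁ on the marrow percentage, with b₁ the PR marrow. Appendix 4 states no reference value, so this is an assumption.

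**Overlap**

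- PR and relapse: [5, 25) ∩ (5, 100] = (5, 25), which is all of PR except exactly 5%.
- On whole percentages, PR holds 20 values (5 to 24) and 19 of them (6 to 24) exceed the relapse limit. On a 0.1% grid it is 199 of 200.
- CR/CRi and relapse: [0, 5) ∩ (5, 100] is empty.

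**Successive marrows in a subject in PR**

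| First | Next | Still in PR range | Above relapse limit | PD (25% rise) |
|---|---|---|---|---|
| 20% | 20% | yes | yes | no |
| 20% | 10% | yes | yes | no |
| 10% | 12% | yes | yes | no (needs 12.5%) |
| 10% | 12.5% | yes | yes | yes |
| 5% | 5% | yes | no | no |

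By threshold, the second row, an improving response, is treated no differently from the fourth, a worsening one.

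**The other two parts of the rule.** PR requires every CR criterion except the marrow one, so a subject in PR has no circulating blasts and no extramedullary disease. Blasts in blood, or disease at an extramedullary site, can therefore genuinely reappear after PR.

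**Timing.** Marrows are scheduled at Cycle 1 Days 8 and 28 and Cycle 2 Day 28 (synopsis, Appendix 2). Section 3.4 allows up to 7 days between cycles. From Cycle 1 Day 28 to Cycle 2 Day 28 is therefore 28 days, or 28 + 7 = 35 at most. After that, marrows are done only when clinically indicated (Sections 3.3.3 and 6.6), with one more at end of treatment (Section 6.7), so there is no fixed next marrow.

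**With the >5% marrow part limited to CR/CRi,** the overlap is empty and no unchanged responder meets the relapse limit.

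**The case against.** The strongest reply rests on the word reappearance: blasts that never cleared cannot reappear, so a stable PR is not a relapse. That is a fair reading, and it rules out saying that the protocol automatically makes every stable PR a relapse, which a reader might infer from the threshold alone. It does not rescue the rule. On that reading the marrow part does nothing for a subject who stays in PR, and the stated limit is still one that the subject's marrow already exceeds.

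A second reply is that adding PR was deliberate, since Appendix 4 lists relapse among its departures from the guideline, and that the addition has content because the blood and extramedullary parts work. Both points stand. The defect is confined to the marrow part.

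A reader might also infer that the trial's survival-type endpoints are distorted. The documents do not support that as a fact. Section 8.5.1 gives methods and censoring, but the events in EFS and RFS and the population for remission duration are not visible. Restriction to CR/CRi may already be the rule. The visible SAP analyses (Section 6.2) are end-of-induction response rates and listings, with no relapse-dated analysis. Nor do the documents show those response rates to be miscounted: a Cycle 2 Day 28 marrow in the PR range still meets the PR definition, whatever second label a site might attach.

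Finally, the conflict over treatment arises only on the threshold reading. Section 6.8 does not list relapse among its discontinuation criteria, and Section 3.3.3 expressly lets PR subjects continue. That limits the conflict, but the synopsis does name relapsed disease as an end of treatment, so the passages still do not agree.

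**Conclusion.** The marrow part of the Appendix 4 relapse rule is wrong as written for subjects in PR. Read by threshold, it covers the whole PR range except exactly 5%; read by reappearance, it has no workable meaning. No other passage settles which reading applies. This finding needs no assumption beyond the stated thresholds.

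The consequences are conditional. An effect on EFS, RFS or cumulative incidence of relapse requires that PR subjects enter those analyses, which cannot be seen. If they do, a PR first seen at Cycle 1 Day 28 could be dated as relapsed 28 to 35 days later whatever the disease does; for a PR first seen at Cycle 2 Day 28 no such interval can be given. The practical reach is also limited because the SAP covers Phase 1b only, for a synoptic report. It merits correction because the correction is cheap and the rule cannot be applied consistently as it stands.

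**What to change.** For endpoint derivation only:

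1. Apply the >5% marrow part of relapse to subjects in CR or CRi.
2. For subjects whose best response is PR, keep reappearance in blood or at an extramedullary site as events. Replacing relapse wholesale by PD would lose the blood part, because a percentage rise from zero circulating blasts is undefined.
3. For those subjects, count marrow worsening by the existing criterion of at least a 25% increase, and state the reference value. The nadir is one option; Appendix 4 already uses it for extramedullary progression.
4. State that RFS and remission duration are for subjects in CR/CRi.

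The SAP is signed, and its introduction provides for later changes to be documented in the CSR, so the rule belongs there. The cost is one derivation rule and a short statement; no new data are needed.

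Changing the relapse definition in Appendix 4 itself would also change what counts as relapsed disease in the synopsis treatment-duration text. The clinical team must therefore reconcile the PR and relapse definitions, Section 3.3.3 and the synopsis. No treatment rule is proposed here.
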